7.3. Procedures for Recording Adverse Events

The side effects of interest will be collected through the completion of the daily diary only.

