5.11. Data Collection - Measurements and follow-up

Nasal sampling (swabs to send for bacteriology/virology) will be optional to maximise the generalisability of the sample, but we envisage from our experience of the TARGET cohort and other studies a high level of acceptance of sampling (at least 80%). The key microbiology of interest is the bacteriology for the common bacterial pathogens since we are interested in exploring whether the presence of pathogens predicts response to antibiotics but we will also aim to store the viral samples for future analysis. Participants will keep a diary of symptoms and daily activities (including days away from work) for up to four weeks after inclusion, and will post the diary back once symptoms have settled. If no diary is received a brief questionnaire will be sent to document the key outcomes (antibiotic use; severity and duration of symptoms), and following this a phone call and/or text to individuals not returning the brief questionnaire.

5.12. OUTCOMES Proposed feasibility outcomes.

- Recruitment rate
- Proportion of eligible patients who accept randomisation
- Proportion using nasal irrigation in the first week in the intervention group
- Proportion using their antibiotic prescription in the intervention group and in the control group
- Proportion followed up with a primary outcome in each group

Proposed clinical outcomes

Antibiotic use: Use of antibiotic prescriptions reported in the 4 weeks of the symptom diary. We anticipate that the intervention will help individuals both decide not to use an immediate prescription if they have been given one and particularly limit the redemption of any delayed prescription. We have shown that the use of delayed prescriptions reported in diaries matches whether they were collected from practices(17).

Secondary outcomes

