5.19 Discontinuation / withdrawal of participants from trial

Each participant has the right to discontinue their study medication or withdraw from the study at any time. In addition, the investigator may discontinue a participant's treatment or withdraw a participant from the study at any time if the investigator considers it necessary (e.g. the participant experiences an adverse reaction, the patient withdraws consent, or the investigator considers that further participant in the study would not be appropriate due to the personal circumstances of the participant).

Patients whose nasal irrigation is discontinued will still be required to complete their study diaries and questionnaires and will still receive telephone follow-up calls unless they choose to withdraw consent for these.

WITHDRAWAL

Once a participant withdraws or is withdrawn from the study, no actions will be taken to obtain data other than to monitor adverse events (see section 7.3. PROCEDURES FOR RECORDING ADVERSE EVENTS). Consent to proceed with reviewing the medical notes will be specifically confirmed for participants withdrawn from the study.

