7. SAFETY REPORTING

All adverse events, for patients randomised into the trial, should be reported from the time the patient signs the informed consent form until one week after randomisation. Depending on the nature of the event the reporting procedures below should be followed.

Any questions concerning adverse event reporting should be directed to the Study coordination centre in the first instance. A flowchart will be provided to aid in the reporting procedures.

Adverse events presenting to the participants GP will be notified by the practitioner. In addition participants will carry a study card which highlights the need to notify their own doctor regarding adverse events. As a final check all participants will be asked to consent to a medical notes review which will take place after study recruitment at a time when any letters will have been returned from out-patient appointments. This enables us to be confident of detecting adverse events which have not been notified using the first two mechanisms. A member of the research team will provide the practice staff with instructions for extraction of data and a form to record the data from participants' medical notes on further antibiotics and other medications prescribed during the 28-day period after study entry.

Adverse Event (AE)	Any untoward medical occurrence in a participant to whom a		
	medicinal product has been administered, including occurrences		
	which are not necessarily caused by or related to that product.		
	These will not be collected for this study.		
Adverse Reaction (AR)	An untoward and unintended response in a participant to an		
	investigational medicinal product which is related to any dose		
	administered to that participant.		
	The phrase "response to a trial intervention" means that a causal		
	relationship between a trial intervention and an AE is at least a		
	reasonable possibility, i.e. the relationship cannot be ruled out. All		
	cases judged by either the reporting medically qualified professional		
	or the Sponsor as having a reasonable suspected causal		
	relationship to the trial qualify as adverse reactions.		
Serious Adverse Event	A serious adverse event is any untoward medical occurrence that:		
(SAE)	results in death		
	is life-threatening		
	 requires inpatient hospitalisation (i.e an overnight stay) or 		
	prolongation of existing hospitalisation		
	 results in persistent or significant disability/incapacity 		

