	 consists of a congenital anomaly or birth defect. 		
	Other 'important medical events' may also be considered serious if		
	they jeopardise the participant or require an intervention to prevent		
	one of the above consequences.		

	NOTE: The term "life-threatening" in the definition of "serious" refers	
	to an event in which the participant was at risk of death at the time	
	of the event; it does not refer to an event which hypothetically might	
	have caused death if it were more severe.	
Serious Adverse Reaction	An adverse event that is both serious and, in the opinion of the	
(SAR)	reporting Investigator, believed with reasonable probability to be due	
	to the trial treatments, based on the information provided.	

Hospitalisations for elective treatment of a pre-existing condition do not need reporting as Serious Adverse Events (SAEs).

The antibiotics used in SNIFSII (beta-lactams or macrolides) are licensed medicines whose most common side-effects are mucocutaneous candidosis (thrush), diarrhoea, nausea, vomiting and rash (occurrence >=1/100 to <1/10). If these occur and are non-serious and of mild to moderate severity (based on clinician's assessment) an Adverse Event Report form will not be necessary. We will collect data on events such as severe reactions to the antibiotics such as anaphylaxis, severe allergy requiring steroid administration, emergency hospitalization for chest problems and severe Clostridium (antibiotic related diarrhoea).

Unexpected adverse reactions to antibiotics will be highly unlikely amongst trial participants, as the vast majority of patients will have previously received antibiotics to treat other infections. For non-serious adverse reactions to trial medication, the Chief Investigator or a designated alternative study clinician will assess the urgency with which the participant's treatment allocation should be unblinded.

For Nasal Irrigation there have been no serious sides effects reported, the most common side effects being nasal stinging and sinus discomfort for some patients.

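### Minor side effects that never reach a clinician have no stated capture route in patients who do not return the diary or who withdraw

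*Protocol*

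**What the plan says.** Section 7.3 of the protocol is a single sentence: "The side effects of interest will be collected through the completion of the daily diary only".

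Section 5.11 has participants keep the diary for up to four weeks; they "will post the diary back once symptoms have settled". For non-return it says: "If no diary is received a brief questionnaire will be sent to document the key outcomes (antibiotic use; severity and duration of symptoms". Those who do not return the questionnaire are then phoned or texted.

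Section 5.19 treats two groups differently. On stopping irrigation: "Patients whose nasal irrigation is discontinued will still be required to complete their study diaries and questionnaires", and calls continue too, unless the patient withdraws consent for these. After withdrawal from the study: "no actions will be taken to obtain data other than to monitor adverse events (see section 7.3. PROCEDURES FOR RECORDING ADVERSE EVENTS". Review of the medical notes then needs specifically confirmed consent.

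Section 7 has routes that do not use the diary. "Adverse events presenting to the participants GP will be notified by the practitioner". Participants also carry a study card prompting them to tell their doctor. A notes review is the final check, of which the protocol says: "This enables us to be confident of detecting adverse events which have not been notified using the first two mechanisms". Section 7.4 has health professionals report serious adverse events within 24 hours of learning of them.

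**The concern.** With the diary as the sole source for the side effects of interest, two groups have no source for minor ones. Diary non-returners are contacted again, but about other things. Withdrawn patients are promised continued adverse-event monitoring through a section that offers only the diary.

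The effects at issue are the mild ones. Section 7 names nasal stinging and sinus discomfort as the commonest effects of irrigation, and mild to moderate thrush, gut upset and rash for the antibiotics. Patients may well not consult for these.

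At stake is the pilot's picture of tolerability. Section 1 lists adherence to and acceptability of the intervention among the feasibility outcomes, and the pilot is meant to support a full-trial application. A side-effect proportion based on returned diaries alone could look better than the truth if patients who tolerate treatment badly return fewer diaries.

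**Working it through.** **1. Do the sections leave a gap?**

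| Patient group | Minor side effect, never presented to a clinician | Event presented to the GP, or serious |
|---|---|---|
| Diary returned | Diary (7.3) | GP, study card, notes review (7); 24-hour report if serious (7.4) |
| Irrigation stopped, still in study | Diary continues (5.19) | As above |
| Diary not returned | None stated: back-up content in 5.11 omits side effects | As above |
| Withdrawn from study | None stated: 5.19 points to 7.3, which names only the diary | GP notification and card; notes review if consent is confirmed |

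The gap is two cells of the table. The neighbouring text does not close it. Section 7 asks for all adverse events to be reported until one week after randomisation, yet its definition table says adverse events are not collected in this study, and 7.3 adds a third rule. The one-week window is also shorter than the irrigation period of up to 21 days in Section 5.7.

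**2. The plan's own figure (Section 5.15)**

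Inputs: 90% against 65% antibiotic use, alpha 0.05 (taken as two-sided), power 80%. The usual normal-approximation formula for two proportions, without continuity correction, gives 43 per group. Allowing for 20% loss: 43 / 0.80 = 53.75, rounded up to 54 per group, 108 in all. The stated figures reproduce and are not in question.

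**3. How many patients could lack these data?**

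The protocol gives no diary-return rate. Assumption: diary non-return equals loss to follow-up.

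- Planned 20% loss: 108 × 0.20 = 21.6, about 22 (11 per arm of 54).
- Lowest follow-up considered, 65%: 108 × 0.35 = 37.8, about 38 (19 per arm).

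Follow-up can also be achieved by questionnaire, call or text, so diary non-return may be higher than these figures.

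**4. What that does to a side-effect proportion**

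Assumed rate among returners: about 10%. The worst-case bounds treat all missing patients in an arm of 54 as without, then with, the side effect.

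- 80% return: 4/43 = 9.3% observed; bounds 4/54 = 7.4% to (4 + 11)/54 = 27.8%.
- 65% return: 4/35 = 11.4% observed; bounds 4/54 = 7.4% to (4 + 19)/54 = 42.6%.

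True rate = r × 10% + (1 − r) × k × 10%, where r is the return rate and k the assumed ratio of the rate in non-returners to that in returners:

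| k | r = 0.80 | r = 0.65 |
|---|---|---|
| 1 | 10% | 10% |
| 2 | 12% | 13.5% |
| 3 | 14% | 17% |

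Diaries alone would show 10% throughout. With k = 1 there is no bias, and the protocol does not say what k is.

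**5. What the back-up contact could recover**

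Patients lost on every route stay missing whatever is asked. The gain lies in those who return no diary but answer the questionnaire or call. As an illustration, with 65% diary return and 80% overall follow-up, 43 − 35 = 8 per arm would answer only the back-up contact. The width of the worst-case bounds would fall from 19/54 = 35.2 to 11/54 = 20.4 percentage points.

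**The case against.** The strongest reply is that the protocol has several safety routes independent of the diary: GP notification, the study card, the notes review, 24-hour reporting of serious events, and collection of severe antibiotic reactions. This stands. A reader might infer that harms in general go unobserved in these patients, or that monitoring after withdrawal would not happen at all. The documents support neither: nothing ends GP notification or the study card at withdrawal, and the notes review remains possible with consent.

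A reader might also infer that those who stop irrigating because of side effects drop out of sight. Section 5.19 says otherwise; they stay on diaries, questionnaires and calls. Where an investigator withdraws someone because of an adverse reaction, the investigator already knows of it.

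Nor does Section 7 clash with a posted diary where it refers to clinician grading: "If these occur and are non-serious and of mild to moderate severity (based on clinician's assessment". That condition only decides whether a report form is needed.

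It can also be said that no side-effect rate is a listed outcome, and that reasons for non-adherence and the interviews address tolerability. This holds in part. The adherence scale is not in the back-up questionnaire's listed content, and 15 to 30 interviews give no rate per arm. Finally, the questionnaire itself is not reproduced in the protocol, so the form in use may ask more than Section 5.11 lists. If so, only the wording needs changing.

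**Conclusion.** The point holds for non-serious side effects that never reach a clinician or the notes, in diary non-returners and withdrawn patients. The wording of Sections 5.11, 5.19 and 7.3 establishes this without any calculation. The cross-reference from 5.19 to 7.3 is defective because it supplies no method that survives withdrawal, and Section 7 contradicts itself on whether adverse events are collected.

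The size is uncertain. The figure of 22 to 38 of 108 patients rests on equating diary non-return with loss to follow-up. The side-effect rates used are illustrations, not protocol figures. That missing patients have more side effects is plausible but not shown. The sample size and the antibiotic-use comparison are unaffected. This is a worthwhile, inexpensive improvement to the tolerability data, not a failure of safety oversight.

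**What to change.** - **Section 5.11:** add the diary's side-effect items, for irrigation and antibiotics and in both arms, to the back-up questionnaire and the call or text script.
- **Section 7.3:** replace the diary-only rule with the diary or, where it is not returned, the questionnaire or call.
- **Section 5.19:** state that withdrawing patients who agree are asked these items once at withdrawal, and that the Section 7 routes continue.
- **Sections 5.19, 7 and 7.3:** reconcile them so that one rule says which adverse events are collected, by which route and over what period.
- **Reporting:** give side effects by arm with the number of patients responding as denominator, and show how many answered by each route.

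The cost is a slightly longer short form, which might lower its return a little, and some retrospective, mixed-mode data. No change to sample size, visits or treatment follows.

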7.4. Reporting Procedures for Serious Adverse Events

Appendix E contains a flowchart summarising the procedure for SAE reporting. Healthcare professionals will report SAEs to the SNIFSII coordination centre within 24 hours of becoming aware of the event. A medically qualified individual will be responsible for assessing the relatedness of the SAE to the trial procedures. All SAEs will be reported using the SAE form either on line or by paper_and reporting this to the SNIFSII coordinating centre. All SAEs will be reported using the. The will SNIFSII coordinator will maintain dedicated report lines with answerphone and fax facilities to allow reporting of SAEs. The answerphone and fax will be checked regularly during office hours.

The Chief Investigator (CI) or their designated representative will be responsible for assessing the expectedness of SAEs reported as being related to the trial. Assessment of expectedness will be based on the Summary of Product Characteristics or the previous evidence about side effects of nasal irrigation. Reporting procedures for Suspected Unexpected Serious Adverse Reactions (SUSARs) are described in section 10.6.

The CI or designated PI at each clinical site will supply any supplementary information as requested by the REC or SNIFSII coordination centre.

7.5. Expectedness

Expectedness will be determined according to the Summary of Product Characteristics for antibiotics and based on prior evidence of side effects of nasal irrigation.

7.6. SUSAR Reporting

All SUSARs will be reported by the CI delegate to the REC and other parties as applicable. For fatal and life-threatening SUSARS, this will be done no later than 7 calendar days after the Sponsor or delegate is first aware of the reaction. Any additional relevant information will be reported within 8 calendar days of the initial report. All other SUSARs will be reported within 15 calendar days.

Principal Investigators will be informed of all SUSARs for the relevant IMP for all studies with the same Sponsor, whether or not the event occurred in the current study.

7.7. Safety Monitoring Committee

The Trial Steering Committee will be responsible for reviewing SAEs after each recruitment season. The main aims of this review are as follows:

- To ensure the safety of each patient in the trial;
- To pick up any trends, such as increases in unexpected events, and take appropriate action;
- To seek additional advice or information from investigators where required;

• To evaluate the risk of the trial continuing and take appropriate action where necessary;

• To act or advise, through the Chairman or other consultant, on incidents occurring between meetings that require rapid assessment.

7.8. Development Safety Update Reports

In addition to the expedited reporting above, the CI shall submit once a year throughout the clinical trial, or on request, a safety report to the Ethics Committee, Host NHS Trust and Sponsor.

7.9 Criteria for the termination of trial

The TSC will review SAEs after each recruitment season. The TSC or Sponsor may advise on whether the trial should be terminated.

8. HEALTH ECONOMICS

We do not propose a formal Economic analysis for the feasibility study, but simply feasibility wok to ensure that cost/resource data can be collected.

We will measure the quality of life based on the EQ5D5L. The EQ5D5L will be included on the basis that it measures quality of life at a point in time, and will be used in conjunction with the clinical outcome measures at days (1,3,7,14,21,28). This is important for an acute condition, and EQ5D was very helpfully used in the GRACE studies in adults to document change over time (and did change significantly which suggests it is likely to be useful in this population too).

9. STATISTICS

9.1. Description of Statistical Methods

The pilot data will examine organisational difficulties, whether fewer than expected eligible patients were recruited, any issues reported by GP regarding patients eligibility, and concerns encountered from patients.(28) Unearthing the key problems for recruiters is of central importance in the piloting phase and we anticipate that the issues will become apparent, as they have in our previous studies, in the process of detailed and sensitive discussion/iteration between an experienced trial manager and the 20-30 recruiting clinicians who are likely to participate in piloting. Based on this we would then make any required adjustments to the recruitment procedures, but no forma statistical analysis will be undertaken.

Statistical analysis.

Analysis of the feasibility outcomes will be descriptive with 95% confidence intervals provided for all proportions of interest, and where relevant also subdivided by trial group (e.g. proportion followed-up; proportion of the intervention group using nasal irrigation, proportion in each group using antibiotics).

We will also provide a table of baseline characteristics by trial group also presented with their 95% confidence intervals, and a similar table of outcomes at follow-up in each trial group for all clinical outcomes with their 95% confidence intervals.

We will do an exploratory intention to treat analysis, blind to group allocation, of the difference in antibiotic use between trial groups using logistic regression controlling for the severity of baseline symptoms, and other potential confounding variables as appropriate. Analysis of duration of symptoms will be performed using Cox proportional hazard models, again controlling for baseline covariates. Kaplan Meier curves will be used to demonstrate the resolution of symptoms graphically. Analysis of symptom severity will use linear regression modelling controlling for baseline covariates.

9.2 The Level of Statistical Significance

A 5% significance level will be used for testing the effects as per the sample size calculation.

9.3. Procedure for Accounting for Missing, Unused, and Spurious Data

For the regression analyses we will impute missing data using multiple imputation if appropriate.

9.4. Inclusion in Analysis

The primary analysis will be an intention to treat basis. A per protocol analysis is unlikely to be very meaningful in the proposed modest sample but we can present estimates for individuals who irrigate more than 50% of the days during the first week.

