5.7. Intervention

1) Control group: immediate antibiotic prescription. We wish to provide some estimate of the reduction in antibiotic possible compared with current practice. Since more than 90% of patients currently receive antibiotic for acute sinusitis the nearest approximation to usual care is a prescription for immediate antibiotics, combined with advice about the use of analgesics. Although the particular antibiotics used is not the focus of this investigation, in line with PHE guidance for primary care we will advise the use of Penicillin V 500mgs QDS (or alternatively Amoxicillin 500mg tds) for 1 week or Clarithromycin 500mg BD also for 1 week if participants are allergic to penicillin.

2) Advice to use nasal irrigation. In addition to the advice in the usual care arm to use simple analgesics participants will be given both written and verbal instructions and given a link to a video clip (uploaded on YouTube: http://www.youtube.com/watch?v=zgvoxkGYSU4) demonstrating how to perform irrigation. They will be asked to irrigate the nose (150 ml through each nostril) daily for up to 21 days or until symptoms settle, and a SinuCleanse 19 nasal cup ('Netipot') will be provided to each subject. Patients will make their own buffered saline irrigation solution every 1 to 2 days comprising: 1 heaped teaspoon salt, one half teaspoon baking soda and 1 pint (568 ml) tap water; how to do this will also demonstrated on the video clip. We chose this particular intervention based on the provisional evidence from a previous randomised controlled trial in primary care in chronic/recurrent sinusitis (11) and from our most recent large trial also in chronic or recurrent sinusitis (13), where most patients found it acceptable and the majority continued using nasal irrigation. Participants in this group will be offered a delayed antibiotic prescription as in our previous trials(19), and advised only to use it if symptoms are getting significantly worse or not even starting to settle a little after a further week.

All study participants in both groups will have access to usual care; further medication or referral will be at the discretion of the doctor according to the normal practice of that doctor.

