6.3. Compliance with Trial Treatment

Patients will be asked to record in their study diaries each time irrigation was used. Patients whose study diaries indicate that they received more than half the intended irrigations during the first week will be considered to be compliant with trial procedures. All randomised trial participants will be included in the intention-to treat population.

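### The first-week adherence cut-off in 9.4 leaves out participants who irrigated daily as asked and stopped because symptoms settled by day 3, and 6.3 words the cut-off differently (minor)

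*Protocol*

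**What the plan says.** Section 5.7 asks the intervention group to "irrigate the nose (150 ml through each nostril) daily for up to 21 days or until symptoms settle", and the table in 6.1 repeats this. The requested course therefore ends at recovery if recovery comes before day 21.

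Two sections then set a 50% cut-off for the first week:

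- Section 6.3 counts irrigations. Patients whose diaries show that they "received more than half the intended irrigations during the first week will be considered to be compliant with trial procedures". It does not say whether the intended number ends when symptoms settle. The source is the diary: "Patients will be asked to record in their study diaries each time irrigation was used".
- Section 9.4 counts days. After making intention to treat the primary basis and stating that "A per protocol analysis is unlikely to be very meaningful in the proposed modest sample", it adds that "we can present estimates for individuals who irrigate more than 50% of the days during the first week".

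Neither section refers to the other, and neither says how to count a participant who stopped because symptoms settled. The related feasibility outcome in 5.12 is "Proportion using nasal irrigation in the first week in the intervention group". It carries no 50% threshold.

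**The concern.** The 9.4 rule has a fixed denominator, while the treatment instruction has a variable length. A participant can do everything asked and still miss the cut-off, purely because recovery came early. Membership of the subset then depends on the course of the illness, which is itself an outcome.

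The direction of the effect can be foreseen. Section 5.7 advises using the delayed prescription only if symptoms get significantly worse or are not starting to settle after a further week. A participant who has settled by day 3 would not ordinarily meet either condition. Removing such people tends to raise both antibiotic use and symptom duration among those left.

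The different wording in 6.3 adds a smaller problem. On one reading of that section, the same participant can be compliant in 6.3 and outside the subset in 9.4.

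**Working it through.** The plan gives no figure here to reproduce. The check compares the two rules and then sizes the affected group.

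**1. The rules for each length of illness.** Let s be the last symptomatic day in week 1 (1 to 7) and k the number of days irrigated. Assume one irrigation a day, stopping when symptoms settle, so k is at most s.

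- 6.3, if the intended number ends at recovery: k > 0.5 × s.
- 6.3, if the intended number is a fixed seven: k > 3.5, so k ≥ 4.
- 9.4: k > 0.5 × 7 = 3.5, so k ≥ 4.

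| s | k passing 6.3 (ends at recovery) | k passing 9.4 |
|---|---|---|
| 1 | 1 | none |
| 2 | 2 | none |
| 3 | 2, 3 | none |
| 4 | 3, 4 | 4 |
| 5 | 3, 4, 5 | 4, 5 |
| 6 | 4 to 6 | 4 to 6 |
| 7 | 4 to 7 | 4 to 7 |

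The rules differ for six patterns (s, k): (1,1), (2,2), (3,2), (3,3), (4,3) and (5,3). All six pass 6.3 and fail 9.4. From s = 6 the rules agree.

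Among participants who irrigated on every symptomatic day (k = s), 9.4 drops only s = 1, 2 and 3. At s = 3 the fractions are 3/3 = 100% and 3/7 = 43%. At s = 4 the 9.4 fraction is 4/7 = 57%, which passes.

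If the intended number is a fixed seven, 6.3 and 9.4 are the same rule, and both drop s = 1, 2 and 3.

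**2. Share settled by day 3.** The protocol gives no distribution of early recovery. Section 3 quotes a median of 2 weeks from a UK primary care trial and of nearly 3 weeks from a systematic review. Taking medians M of 14 and 21 days from randomisation, with assumed shapes:

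| Assumed shape | Formula | M = 14 | M = 21 |
|---|---|---|---|
| Exponential | 1 − 2^(−3/M) | 13.8% | 9.4% |
| Weibull, shape 2 | 1 − 2^(−(3/M)²) | 3.1% | 1.4% |
| Log-normal, log-SD 1.0 | Φ(ln(3/M)/1.0) | 6.2% | 2.6% |
| Log-normal, log-SD 0.5 | Φ(ln(3/M)/0.5) | 0.1% | <0.1% |

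The range is about 0% to 14%. The top value is 0.138 × 54 = 7.5 of the 54 recruited per arm (108/2), or 0.138 × 43 = 5.9 of the 43 expected after the 20% loss allowed in 5.15.

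Section 3 does not say whether its medians run from onset. If they do, and entry is at day 7 of illness, the share settling within 3 days is (S(7) − S(10))/S(7), where S is the proportion still ill. The Weibull and log-normal shapes above then give about 16% to 18% for M = 14 and 6% to 11% for M = 21.

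**3. Illustrative effect on antibiotic use.** Start from the 65% planned in 5.15. Suppose a fraction f is dropped, none of them used antibiotics, and everyone else stays. The subset figure is 0.65/(1 − f).

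- f = 0.138: 0.65/0.862 = 75.4%.
- f = 0.031: 0.65/0.969 = 67.1%.
- f near 0: 65%.

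That no dropped participant used antibiotics is an assumption at the extreme. The protocol has no figure for it.

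**The case against.** **The two sections may not conflict.** Section 6.3 does not say that the intended number shrinks at recovery. Once daily for a week is seven, more than half is at least four, and 9.4 says the same. A reader might infer that the protocol contains two incompatible definitions, but the text does not establish that. The conflict exists on one reading only and disappears for anyone symptomatic through day 6. The fixed-seven reading does not clear the plan, however, because both rules then leave out participants who followed the stopping instruction.

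**Little depends on it.** This stands. The 9.4 estimate is optional and comes after intention to treat, and the protocol itself discounts it. Section 9.4 labels nobody non-adherent; it selects a subset. A reader might also infer that the feasibility result on irrigation use is corrupted, but the 5.12 outcome uses neither cut-off.

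**Not everyone who settles by day 3 is affected.** Correct. Someone who irrigates on 1 of 3 symptomatic days fails both rules, and someone who carries on to day 4 passes both. The shares above are therefore upper limits for each assumed shape.

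**This belongs in the analysis plan.** Detail on early stoppers could be left there. But the protocol itself states the cut-off, and that cut-off conflicts with its own instruction.

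**A denominator that ends at recovery also depends on outcome.** This is the strongest point. One irrigation followed by recovery would count as 100%. With a 70% chance of irrigating each day, a 3-day course qualifies with probability 3 × 0.7² × 0.3 + 0.7³ = 78%, and a 7-day course (at least 4 of 7) with 87%. With a 10% daily chance of giving up after the first irrigation, a 1-day course qualifies with 100% and a 7-day course with 0.9³ = 73%. Some selection therefore remains, in a direction that depends on how people lapse. Under the seven-day rule, people who stop on settling by day 3 qualify with 0%. The objection limits what the fix can claim but does not favour the present rule.

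**Conclusion.** The point holds as a minor defect in a stated rule. Under 9.4, a participant who irrigated every day as asked and stopped because symptoms settled by day 3 cannot enter the subset. Section 6.3 does the same if the intended number is a fixed seven. If it ends at recovery, the two sections classify some participants who settle by day 5 differently, always as compliant in 6.3 and outside 9.4.

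The subset estimate may therefore overstate antibiotic use and symptom duration. The size rests on assumed recovery shapes: about 0% to 14% of the intervention group with the quoted medians counted from randomisation, and possibly somewhat more if those medians run from onset. The direction rests on early recoverers having least reason to use the delayed prescription. The documents do not support saying that every dropped participant was antibiotic-free.

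**What to change.** Use one analysis definition in 6.3 and 9.4: days irrigated, divided by days from randomisation to the earlier of day 7 or the diary-recorded day on which symptoms settled; adherent if more than 50%. Define the settling day by a named symptom endpoint already in 5.12. That section has two (the end of moderately bad illness, and symptoms rated very little or no problem) and ties neither to stopping irrigation, so the choice must be written down. Show the fixed seven-day proportion alongside as a descriptive figure.

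Label the subset estimate exploratory. It is still selected after randomisation, and very early recoverers have fewer days on which to fail.

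The cost is wording in two sections and one derived variable, the settling day, for each intervention participant. The diary already records each irrigation and the symptoms. No treatment instruction changes.
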